4.2 Analysis of the Secondary Endpoints

Overall Survival

The event is death from any cause. Overall survival (OS) time will be calculated as the time from randomization on the BMT CTN 0702 protocol to death, loss to follow-up or the end of the study, whichever comes first. CIBMTR data will be used to supplement BMT CTN 0702/07LT data. Patients alive at the time of last observation or lost to follow-up will be censored at the date of last contact either for CIBMTR-reported data or 0702/07LT-reported data. The Kaplan-Meier estimate of survival will be estimated at 5 years post randomization on the BMT CTN 0702 protocol along with corresponding 98.3% confidence intervals. Overall survival will be compared between treatment arms using a stratified two-sided log-rank test in pairwise comparisons of treatment groups. The analysis population will be the 0702-enrolled population, with data from CIBMTR included.

Event-Free Survival

Event-free survival (EFS) time will be calculated as the time from randomization on the BMT CTN 0702 protocol to death, progression, second primary malignancy, loss to follow-up or the end of the study, whichever comes first. Patients alive at the time of last observation or lost to follow-up will be censored at the date of last contact. The analysis population will be the 0702-enrolled population with follow up data from the CIBMTR included as needed. The Kaplan-Meier estimate of EFS will be estimated at 5 years post randomization on the BMT CTN 0702 protocol along with corresponding 98.3% confidence intervals. Event-free survival will be compared between treatment arms using a stratified, two-sided log-rank test in pairwise comparisons of treatment groups.

Second Primary Malignancies

The event is the development of the first SPM post randomization on BMT CTN 0702, excluding non-melanoma skin cancers. Death without SPMs will be considered a competing risk for this event. The analysis population is the 0702-enrolled population, and CIBMTR data will be used to supplement BMT CTN 0702/07LT data. Start time is randomization on BMT CTN 0702. Cumulative incidence function will be used to calculate this endpoint and time of randomization on the BMT CTN 0702 protocol will be the starting point for the analysis. Estimates at 5 years will be described along with 98.3% confidence intervals. The cumulative incidence of SPMs will be compared between treatment arms using stratified two-sided Gray's test in pairwise comparisons of treatment groups. SPMs will also be described by histologic type. It will be

noted that reporting of SPM is not required after progression, and the CIBMTR data will be used to supplement 07LT data.

Unexpected Grades 3-5 Adverse Events

Unexpected grades 3-5 adverse events occurring post enrollment on BMT CTN 07LT will be tabulated and compared across treatment arms and lenalidomide status for participants enrolled in BMT CTN 07LT. CIMBTR data will not be used. AEs will be described using the Medical Dictionary for Regulatory Activities (MedDRA) and classified according to the system organ class and preferred term. Summaries by type and severity by treatment arm will be provided, and tabulations will be separated into tables for those who initiated maintenance on BMT CTN 07LT and those who did not.

Health Quality of Life

Health quality of life (HQL) will be compared between all treatment groups utilizing the FACT-BMT self-report, transplant-specific questionnaire and the generic quality of life tool, the SF-36. Only English and Spanish speaking patients are eligible to participate in the HQL component of this trial. Participants were not required to complete the HQL questionnaires after progression; therefore, only HQL completed prior to progression will be summarized. The limitations in interpretation of this analysis will be noted with the presentation of the results. HQL at each time point from BMT 0702 baseline through 5 years post randomization on BMT CTN 0702 will be summarized using simple descriptive statistics (median, mean, SD or SE). No formal statistical analyses will be conducted. As 5 year data is only available for those participants on 07LT, this analysis will focus solely on 07LT participants.

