### **3.3.2. Event-free Survival**

Event-free survival (EFS) time will be calculated as the time from randomization on the BMT CTN 0702 protocol until death from any cause, disease progression, or second primary malignancy, whichever comes first. Patients alive at the time of last observation or lost to follow-up will be censored at the date of last contact. Event-free survival will be compared between treatment arms once all alive patients have been followed for 5-years post randomization on the BMT CTN 0702 protocol.

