2.2 Handling Missing Data

All participants who were randomized on the parent protocol BMT CTN 0702 will be included in the analysis for BMT CTN 07LT. Data for patients not enrolled on the long-term follow-up protocol will be included with two parts combined: 1) 0702 data until their end of participation on the BMT CTN 0702 protocol; 2) follow up data provided through the Center for International Blood and Marrow Transplant Research (CIBMTR).

For time-to-event variables, participants who have not had an event or competing risk event will be censored at the time data for the endpoint is no longer available. For Quality of Life analyses, participants will be excluded at a particular time point if they do not complete the surveys within a +/- 90-day window for the particular time point in the analysis.

The time of progression that was adjudicated on BMT CTN 0702 by the 0702 Endpoint Review Committee (ERC) will be used for participants who progressed on BMT CTN 0702. There is no adjudication of progression on BMT CTN 07LT, so progression will be determined by site-reported responses.

For the primary endpoint of PFS and the secondary endpoints of EFS, overall survival and cumulative incidence of SPM, and for tabulation of cause of death, data from the BMT CTN 0702, BMT CTN 07LT, and from the CIBMTR will be used.

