4.1 Analysis of the Primary Endpoint

The primary analysis of PFS will include all randomized subjects from the BMT CTN 0702 protocol, classified according to their randomized treatment allocation, irrespective of treatment received [intent-to-treat]. The time to this event is the time from randomization on the BMT CTN 0702 protocol to progression, initiation of non-protocol anti-myeloma therapy (this includes lenalidomide if the dose is above 15mg), or death from any cause reported on BMT CTN 0702, BMT CTN 07LT, or to the CIBMTR. Patients will be censored at loss to follow-up or end of 2018, whichever comes first. For those lost to follow-up, if loss occurred during 0702, censoring will occur at last myeloma evaluation before loss to follow-up. For those lost to follow-up on BMT CTN 07LT, censoring will occur at the last contact date reported on the study status follow-up form. For those who completed BMT CTN 0702 but did not enroll on 07LT, censoring will occur at the last evaluation of progression provided by the CIBMTR.

The treatment arms will be compared with a two-sided log-rank test stratified on risk status. Tests will be performed pair-wise at the 0.05/3 level to maintain type I error at 0.05 for this endpoint in this analysis. A Kaplan-Meier plot of PFS and 5-year estimates of PFS will be provided by treatment group.

A secondary analysis of PFS will be conducted using Cox regression, with treatment arm and risk strata as covariates, and adjusting for demographic and baseline characteristics which are statistically different between treatment arms (p<0.1) for covariates specified in section 3.1. Start time will be randomization on BMT CTN 0702.

In another secondary analysis of PFS, discontinuation of lenalidomide maintenance will be considered as a time-varying covariate in a separate Cox regression model for those who initiated lenalidomide; in this model, the outcome will be the time to progression or death from initiation of lenalidomide. Initiation of maintenance lenalidomide on BMT CTN 0702 will be the start time for this analysis. CIBMTR data will be used to determine whether participants who discontinued study lenalidomide also discontinued commercial lenalidomide. The limited interpretation will be noted for this analysis, since it will include non-randomized comparisons and there may be bias in who enrolled in BMT CTN 07LT.

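### EFS is censored at last contact although it includes progression, while PFS stops at the last disease evaluation for patients lost during 0702 or not enrolled on 07LT; 5-year EFS tends to be overstated when contact outlasts evaluation

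*SAP*

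**What the plan says.** EFS runs from randomization on 0702 "to death, progression, second primary malignancy, loss to follow-up or the end of the study, whichever comes first" (SAP 4.2). Protocol 3.3.2 sets one censoring rule for everyone without an event: "Patients alive at the time of last observation or lost to follow-up will be censored at the date of last contact". Protocol 5.4 and SAP 4.2 repeat it. In SAP 4.2 these patients will be "censored at the date of last contact. The analysis population will be the 0702-enrolled population with follow up data from the CIBMTR" added as needed.

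For PFS, SAP 4.1 sets the censoring date by follow-up source:

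- Lost to follow-up in the parent trial: "if loss occurred during 0702, censoring will occur at last myeloma evaluation before loss to follow-up".
- Completed 0702 but "did not enroll on 07LT, censoring will occur at the last evaluation of progression provided by the CIBMTR".
- Lost on 07LT: the last contact date on the study status follow-up form.

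The notes to Exhibit 07LT-3 give a single PFS rule, the date of last myeloma data from any of the three sources. SAP 2.2 gives a general rule for time-to-event variables: participants without an event "will be censored at the time data for the endpoint is no longer available".

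**The concern.** Progression is part of both endpoints and depends on the same disease evaluations. A registry report that a patient is alive does not show that the patient is progression-free. Last contact is the natural rule for OS, and the EFS sentence appears to have been carried over from there: the censoring wording matches the OS paragraph, and the Event-Free Survival paragraph of Protocol 5.4 ends by saying that overall survival will be compared. SAP 2.8.1, which lists clarifications to the protocol, gives no reason for treating EFS differently from PFS.

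If SAP 4.2 is programmed as written, some patients stay in the EFS risk set during time when a progression could not have been recorded. The 5-year Kaplan-Meier estimate, the log-rank tests, the EFS Cox models, the progression part of the cause-specific models and the EFS landmark analysis all inherit this. The landmark is the most exposed. It estimates 5-year EFS from year 4, which is where 0702 follow-up ends (Protocol 2.3.1).

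**Working it through.** **1. The rules side by side**

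| Patient without an event | PFS censored at (SAP 4.1) | EFS censored at (SAP 4.2) |
|---|---|---|
| Lost during 0702 | last myeloma evaluation | last contact |
| Completed 0702, not on 07LT | last CIBMTR progression evaluation | last contact |
| Lost on 07LT | last contact | last contact |

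The mismatch is confined to the first two rows. Take a patient in the second row, last evaluated at 4.0 years and last known alive at 5.0 years. PFS is censored at 4.0 and EFS at 5.0, so one year is counted as event-free although progression was not assessed.

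**2. The plan's own figures**

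SAP 2.1 projects 417 to 569 patients on 07LT. This reproduces: 758 × 0.55 = 416.9, rounded up to 417, and 758 × 0.75 = 568.5, rounded up to 569. The level 0.05/3 = 0.01667 matches the 98.3% intervals. The documents give no EFS assumption, no number of registry-followed patients and no gap between last evaluation and last contact. The size below is therefore an illustration.

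**3. Inputs of the simulation**

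Only the 3-year PFS range of 55–75% comes from the documents (55%, 65% and 75% were used). The rest is assumed:

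- exponential times;
- death without progression 0.01 per year, second malignancy 0.012 per year, death after progression 0.12 per year;
- 10%, 25% or 40% of patients followed by the registry after year 4;
- last progression evaluation for them at year 4, or uniform over years 4 to 5;
- contact for a further 0.5 or 1 year;
- administrative end uniform between 5 and 8.5 years;
- second malignancy and death seen up to last contact.

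This gives 3 × 3 × 2 × 2 = 36 scenarios of 400,000 patients each. Patients lost during 0702 were not modelled.

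Progression hazard = −ln(3-year PFS)/3 − 0.01. At 55% this is 0.1993 − 0.01 = 0.1893. True 5-year EFS = exp(−5 × (0.1893 + 0.01 + 0.012)) = exp(−1.0564) = 0.348, and the simulation agrees.

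**4. Results for 5-year EFS**

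| 3-year PFS | Registry share | Last evaluation | Gap | True | Last contact | Last evaluation rule |
|---|---|---|---|---|---|---|
| 75% | 10% | years 4–5 | 0.5 y | 58.3% | 58.5% | 58.2% |
| 65% | 25% | years 4–5 | 1 y | 45.9% | 46.7% | 45.7% |
| 55% | 40% | year 4 | 1 y | 34.8% | 37.5% | 34.1% |

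The last-contact rule overstated 5-year EFS in all 36 scenarios: by 0.2 to 1.4 points when the last evaluation fell in years 4 to 5, and by 0.2 to 2.7 points when it fell at year 4. EFS time exceeded PFS time in 4% to 26% of randomised patients. In the bottom row, PFS under the SAP 4.1 rule was 36.5%, below the 37.5% for EFS, although the simulated EFS counts every PFS event plus second malignancies.

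**5. Hand check of the largest case**

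If nothing at all were recorded for the registry group between years 4 and 5, the overstatement would be 0.4 × (exp(−4 × 0.2113) − exp(−5 × 0.2113)) = 0.4 × (0.4295 − 0.3477) = 0.033, or 3.3 points. The simulated 2.7 lies below this because second malignancies and deaths are still seen.

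**6. Against the planned precision**

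For about 250 patients per arm and EFS of 50%, the 98.3% half-width is at least 2.394 × √(0.25/250) = 0.076, or 7.6 points.

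**The case against.** The strongest reply is that SAP 2.2 already censors when endpoint data run out, and that the same section names EFS among the endpoints built from all three data sources. The OS paragraph of SAP 4.2 spells out last contact from either source; the EFS paragraph does not, and brings in registry data only where needed. So it is an inference that EFS runs on to the last registry contact. This shows that the plan is ambiguous, but it does not cure the problem: the specific EFS sentence says last contact, and a programmer following SAP 4.2 would use it.

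The size can also be challenged, fairly. The projection of 417 to 569 amounts to every progression-free patient enrolling on 07LT, which would leave few registry-only patients who are still event-free. But the plan itself provides for patients who do not enrol (SAP 2.2, SAP 4.1, Exhibit 07LT-1), without saying how many there are.

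Last contact is reasonable for deaths and second malignancies, which can be learned at contact. That part of the objection stands.

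A reader might infer four stronger things that the documents do not support:

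- **EFS time can never exceed PFS time.** The EFS text in SAP 4.2 omits non-protocol anti-myeloma therapy, which PFS counts; only the Exhibit 07LT-6 shell includes it. On the written text, EFS can outlast PFS under any censoring rule.
- **All patients are affected.** Patients lost on 07LT are censored at last contact for both endpoints.
- **Some arms are favoured.** Nothing shows that registry-only follow-up differs by arm; with similar shares the effect would largely cancel in the pairwise tests. The same condition applies to the lenalidomide groups in the landmark.
- **Large errors at later times.** The planned EFS estimate is at 5 years only.

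**Conclusion.** The point holds as a conflict between stated rules with a known direction and a small, uncertain size. For patients lost during 0702 and for 0702 completers not on 07LT, the written EFS rule counts unassessed time as progression-free. Five-year EFS then tends to be overstated, by about 0.2 to 2.7 percentage points on the assumptions listed, and by nothing if there is no gap before year 5. That is well inside the planned confidence interval, but it is systematic and avoidable. The primary PFS analysis is not affected. A distortion of comparisons between arms or lenalidomide groups is possible only if registry-only follow-up is unequal.

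**What to change.** In SAP 4.2 and Protocol 3.3.2 and 5.4, censor EFS by follow-up source on the PFS dates of SAP 4.1: last myeloma evaluation if lost during 0702, last CIBMTR progression evaluation if not enrolled on 07LT, and the SAP 4.1 rule for 07LT patients. Bring SAP 2.2, 4.1, 4.2 and the notes to Exhibit 07LT-3 into agreement; the exhibit and SAP 4.1 now differ for patients lost on 07LT. State whether deaths and second malignancies after the last evaluation count as EFS events. Make the EFS text and the Exhibit 07LT-6 shell agree on non-protocol therapy.

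Apply the rule to Exhibit 07LT-6, Supplemental Exhibits 07LT-6A and 6C, the progression model in 6B, and the EFS landmark (Supplemental Exhibit 07LT-8). Keep last contact for OS and for the separate second-malignancy and death models in 6B, and add EFS with last-contact censoring as a sensitivity analysis.

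The cost is wording and one extra run, since the PFS censoring dates are needed anyway. EFS follow-up becomes slightly shorter. If later deaths or second malignancies still count, a small opposite bias is possible: about 0 to −1 point across the 36 scenarios. The change therefore reduces the error but does not guarantee an unbiased estimate.

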### 4.3. Adverse Event Reporting

#### 4.3.1. Unexpected, Grades 3-5 Adverse Events

Reporting of Adverse Events (AE) in the long-term follow-up protocol will follow the same mechanism as the BMT CTN 0702 parent clinical trial for patients receiving long-term lenalidomide maintenance therapy. AEs will be reported according to the BMT CTN Manual of Procedures. The BMT CTN Data and Safety Monitoring Board (DSMB) will be responsible for the safety and oversight of this long-term follow-up protocol. Unexpected, grades 3-5 adverse events will be reported through the expedited AE reporting system in AdvantageEDC using NCI's Common Terminology Criteria for Adverse Events (CTCAE) Version 4.0. Unexpected, grade 4-5 AEs must be reported within 24 hours of knowledge of the event. Unexpected, grade 3 AEs must be reported within three business days of knowledge of the event.

The descriptions and grading scales found in the NCI Common Terminology Criteria for Adverse Events (CTCAE) Version 4.0 will be utilized for AE reporting and can be found at [http://evs.nci.nih.gov/ftp1/CTCAE/CTCAE\\_4.03\\_2010-06-14\\_QuickReference\\_5x7.pdf](http://evs.nci.nih.gov/ftp1/CTCAE/CTCAE_4.03_2010-06-14_QuickReference_5x7.pdf).

Selected expected serious AEs (Appendix F - Table F-1) require expedited reporting with an Individual Case Safety Report (ICSR). Additionally, selected AEs of interest (Appendix F - Table F-2) will require expedited reporting through an ICSR, if they fulfill serious criteria according to the Code of Federal Regulations Title 21 (21 CFR 312.32) and occur after the administration of lenalidomide and up to 30 days after the permanent discontinuation of lenalidomide. See Appendix F for additional details on expedited reporting.

The aforementioned adverse event reporting criteria are for patients who receive long-term lenalidomide maintenance therapy. Patients not eligible for receiving long-term lenalidomide maintenance therapy or patients who have permanently discontinued lenalidomide maintenance will not require reporting of unexpected grades 3-5 adverse events or ICSRs with the exception of second primary malignancies as noted in 4.3.2. All patients will be required to report deaths as noted in section 4.3.3.

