#### 4.3.2. Reporting Second Primary Malignancies

All second primary malignancies (SPM), excluding non-melanoma skin cancers, experienced by patients enrolled on the long-term follow-up study will be reported using the Adverse Event forms (AE1-AE6) in AdvantageEDC and must be reported within three business days of knowledge of the event. The Event Description of the Adverse Event forms should include

histologic type. Patients who do not consent or who have progressed on the BMT CTN 0702 protocol will have SPMs reported through the standard CIBMTR reporting mechanism.

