1.5 Response Variables and Data Collection Time Points

Participants are evaluated for the primary endpoint of progression-free survival (death, disease progression, initiation of non-protocol myeloma therapy) and for the following secondary endpoints:

- Overall survival
- Event-free survival (no progression, death, or SPM)
- Incidence of SPM
- Unexpected grades 3-5 adverse events
- Health quality of life

Patients have visits every six months until death, progression, withdrawal of consent, or the end of the study.

Participants who receive long-term lenalidomide maintenance therapy are required to report unexpected grades 3-5 adverse events until the patient progresses or until 28 days from their last dose of lenalidomide. These require expedited reporting within 24 hours – 3 business days of the site's knowledge of the event, depending on the type of event. The protocol specifies additional rules for reporting requirements of AEs after an SPM depending on the treatment received for the SPM, and for reporting serious expected adverse events and selected AEs of interest.

Participants who do not receive lenalidomide maintenance or have permanently discontinued lenalidomide maintenance not required to report adverse events except for SPMs.

For all participants on 07LT, SPMs must be reported within three business days of knowledge of the event and deaths must be reported within 24 hours of knowledge of the participant's death. Non-melanoma skin cancers are not required to be reported.

Health quality of life surveys are completed at visits corresponding to 5, 6, and 7 years from original randomization on 0702.

2. General Statistical Considerations

Unless stated otherwise:

- For continuous outcomes, descriptive statistics will include the number of subjects (n), mean, standard deviation, median, minimum and maximum.
- For categorical outcomes, frequencies and percentages will be displayed for categorical data.
- All statistical comparisons made using 2-sided pairwise tests will be compared to an α =0.05/3 significance level.

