2.7.2 Safety Analysis and Analysis Population

The 07LT-enrolled population is comprised of two groups of participants – those who are taking long-term lenalidomide maintenance therapy, and those who have never started maintenance therapy. Safety data is collected differently for participants taking lenalidomide and or patients who never stated lenalidomide on 07LT or discontinued it.

For participants enrolled on BMT CTN 07LT who are taking long-term lenalidomide maintenance therapy, unexpected, grades 3-5 adverse events will be reported through the expedited AE reporting system in AdvantageEDC using NCI's Common Terminology Criteria for Adverse Events (CTCAE) Version 4.0. Unexpected, grade 4-5 AEs must be reported within 24 hours of knowledge of the event. Unexpected, grade 3 AEs must be reported within three business days of knowledge of the event. Selected expected serious AEs (protocol Appendix F - Table F-1) require expedited reporting. Additionally, selected AEs of interest (protocol Appendix F - Table F-2) will require expedited reporting, if they fulfill serious criteria according to the Code of Federal Regulations Title 21 (21 CFR 312.32) and occur after the administration of lenalidomide and up to 30 days after the permanent discontinuation of lenalidomide. See protocol Appendix F for additional details on expedited reporting.

For participants enrolled on BMT CTN 07LT follow-up only, or for BMT CTN 07LT participants who have permanently discontinued lenalidomide maintenance for more than 28-30 days, or for participants who have met the protocol defined definition of progression, reporting of

unexpected grades 3-5 adverse events, selected serious AEs, or selected AEs of interest will not require reporting with the exception of second primary malignancies.

Deaths are required to be reported for all patients enrolled on 07LT within 24 hours of the site's knowledge of the patient's death.

Unexpected grades 3-5 adverse events will be tabulated and compared across treatment arms for the BMT CTN 07LT population. Summaries by type and severity of adverse events will be provided. Safety data will be summarized using Medical Dictionary for Regulatory Activities (MedDRA) Coding Version 20.0 or above.

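### SAP 4.2 plans to compare unexpected grade 3-5 adverse events by lenalidomide status, although sites need not report them off 07LT study lenalidomide

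*SAP*

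**What the plan says.** **The planned comparison.** SAP 4.2 states: "Unexpected grades 3-5 adverse events occurring post enrollment on BMT CTN 07LT will be tabulated and compared across treatment arms and lenalidomide status". SAP 2.7.2 gives a version by arm only: "Unexpected grades 3-5 adverse events will be tabulated and compared across treatment arms for the BMT CTN 07LT population". Protocol 5.4 also compares by arm only, and SAP 2.8.1 does not list lenalidomide status among the changes from the protocol. For the source of the data, SAP 4.2 adds: "CIMBTR data will not be used".

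**The reporting rule.** Protocol 4.3.1 says that "patients who have permanently discontinued lenalidomide maintenance will not require reporting of unexpected grades 3-5 adverse events", with SPMs excepted, and applies the same exemption to patients not eligible for the drug. SAP 1.5 agrees: "Participants who do not receive lenalidomide maintenance or have permanently discontinued lenalidomide maintenance not required to report adverse events except for SPMs". Two items are collected from everyone on 07LT. For deaths, protocol 4.3.1 says: "All patients will be required to report deaths as noted in section 4.3.3". For SPMs, protocol 4.3.2 says that those "experienced by patients enrolled on the long-term follow-up study will be reported using the Adverse Event forms".

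**What the SAP does about it.** SAP 2.7.2 acknowledges that safety data are collected differently on and off the drug. SAP 4.2 says that "tabulations will be separated into tables for those who initiated maintenance on BMT CTN 07LT and those who did not". These are Exhibits 9A and 9B. A footnote to 9A says that reporting requirements differ; 9B has no footnote.

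**The concern.** One side of the comparison by status is collected by obligation and the other only if a site volunteers it. With no outside source to fill the gap, participants off study drug would appear to have fewer unexpected grade 3-5 events whatever their true risk. A reader of the safety section could take this as evidence about lenalidomide. If risk were really higher off drug, the table could show the opposite.

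The SAP limits the interpretation of its quality-of-life summary (4.2) and of its Cox models with lenalidomide discontinuation as a covariate (4.1 and the third EFS model in 4.3). It attaches no such limit to the adverse event text in 4.2.

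**Working it through.** The documents give no sample size, power or expected rate for this analysis, so there is no figure to reproduce. The check sets the passages side by side; the arithmetic only illustrates.

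**1. Who must report what on 07LT**

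| Participant | Unexpected grade 3-5 AEs | SPMs | Deaths |
|---|---|---|---|
| On 07LT study lenalidomide | required | required | required |
| Never started it on 07LT | not required | required | required |
| Permanently stopped it | not required after the reporting window | required | required |

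Sources: protocol 4.3.1, 4.3.2 and 4.3.3; SAP 1.5 and 2.7.2. The status comparison sets the first row against the others.

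**2. Effect on a comparison by status.** Let v be the fraction of off-drug, non-SPM, non-fatal events that sites report voluntarily. Take on-drug reporting as complete and each patient as wholly on or off drug. Then

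observed off/on ratio = v × true off/on ratio.

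| v (assumed) | true ratio 1 | true ratio 2 |
|---|---|---|
| 0 | 0 | 0 |
| 0.10 | 0.10 | 0.20 |
| 0.25 | 0.25 | 0.50 |
| 0.50 | 0.50 | 1.00 |

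A true doubling off drug would look like a deficit for any v below 0.50.

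**3. Effect on a pooled comparison by arm (SAP 2.7.2 read literally).** With on-drug shares a and b in two arms and equal true risk, the observed ratio is (a + (1−a)v) / (b + (1−b)v).

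- Equal shares, 0.65 and 0.65: 1.00 for any v, so no distortion.
- 0.60 and 0.65: 0.60/0.65 = 0.92 at v = 0; 0.80/0.825 = 0.97 at v = 0.50.
- 0.60 and 0.70: 0.60/0.70 = 0.86 at v = 0; 0.80/0.85 = 0.94 at v = 0.50.

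The shares are assumed; the documents do not give them. Exhibits 9A and 9B do not show such a pooled table.

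**4. The table shells.** In both exhibits the columns are arms, and the row for all events is set to 100.0%. The percentages are therefore shares of events, not of patients at risk. Exhibit 9A is defined by starting lenalidomide on 07LT, so it also covers time after a participant stopped, when reporting lapses.

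**5. End of AE reporting at progression (minor).** SAP 1.5 ends the duty at progression or 28 days after the last dose. Protocol 4.3.1.1 keeps it running after progression until the patient is more than 28 days from the last dose. The gap is at most 28 days per patient who progresses on drug. At an assumed 5 to 20% progressing per year, that is 28/365.25 × 0.05 = 0.4% to 28/365.25 × 0.20 = 1.5% of on-drug time. The 30 days in protocol 4.3.1 against 28 days in Table F-2 concerns AEs of interest and does not affect this analysis.

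**6. SPM reporting after progression (minor).** SAP 4.2 and the Exhibit 8 footnote say that it is not required. Protocol 4.3.1.1 says that it continues to the end of study follow-up. Protocol 4.3.2 and SAP 1.5 require it for all 07LT participants, and SAP 2.7.2 keeps SPMs as the exception for those who have progressed. However, protocol 4.2.1 ends visits at progression, 4.4.1 and 4.4.2 end evaluations there (SPM evaluation included), and 4.4.3 sends later outcomes through CIBMTR. The conflict therefore lies partly inside the protocol.

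**The case against.** The strongest reply is that no planned output contains the contrast. The tables are split by initiation, their columns are arms, no shell puts on-drug beside off-drug, and no test is named. The SAP discloses the differing collection in 1.5, 2.7.2 and the 9A footnote. The ratios above come from an identity and an assumed v. Within 9B the reporting rule is the same for every arm.

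Most of this stands, and it limits the harm to a misleading description. It does not remove the point. The text of SAP 4.2 still commits to comparing across status, and SAP section 5 says that the shells are illustrative and may change, so they cannot override the text. The 9A footnote does not say that off-drug events were not required, and 9B says nothing.

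Three stronger readings are tempting, and the documents do not support them:

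- A reader might infer that the plan will produce a false statistical finding on lenalidomide safety. No test by status is specified.
- A reader might infer that the comparison of arms is biased. That needs on-drug shares that differ by arm in a pooled table; the documents give no shares, and the split tables largely avoid the problem.
- A reader might infer that the SAP simply misstates the SPM rule. Its sentence has support in protocol 4.4.3, and SAP 2.2 pools 0702, 07LT and CIBMTR data for SPMs. The likely consequence is a limitation described wrongly.

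A further caution: off study lenalidomide does not mean unexposed. SAP 1.2.2, 4.1 and Supplemental Exhibit 07LT-3 all allow for commercial lenalidomide.

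**Conclusion.** The concern holds for the comparison by lenalidomide status. As written, SAP 4.2 plans a contrast that would mainly reflect who had to report. The direction is clear from the documents, provided that voluntary reporting off drug is incomplete: off-drug counts would be too low. The size is not known, because it rests on an assumed v.

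The consequence is confined to descriptive safety reporting; the primary PFS analysis is not touched. The two progression-related conflicts are minor. The part of the Exhibit 8 footnote that concerns 0702 cannot be checked, because the parent protocol is not among these documents.

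**What to change.** 1. In SAP 4.2, delete lenalidomide status from the adverse event comparison.
2. In SAP 2.7.2 and 4.2, limit the comparison of arms to participants who started lenalidomide on 07LT. Count events within the required reporting period, and show patients with at least one event over patients who started. List this in SAP 2.8.1, because protocol 5.4 states the comparison by arm without the restriction.
3. Keep Exhibit 9B as a descriptive listing. Add a footnote that these events were not required from participants not on 07LT study lenalidomide, that some of them may have taken commercial lenalidomide, and that only SPMs and deaths were required.
4. Reconcile the end of AE reporting at progression between SAP 1.5 and protocol 4.3.1.1, so that the reporting period in item 2 has one definition.
5. Reconcile the SPM sentence in SAP 4.2 and the 07LT part of the Exhibit 8 footnote with protocol 4.3.1.1 and 4.3.2 and SAP 1.5 and 2.7.2, together with protocol 4.2.1, 4.4.1, 4.4.2 and 4.4.3, so that the limitation is described correctly.

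The cost is SAP wording, two table shells, footnotes and one entry in SAP 2.8.1. Items 4 and 5 may also need a short protocol clarification. No new data are needed. The comparison by status is lost, but the data cannot support it, and voluntary reports stay visible in 9B.
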